In Phase 1 of the study, two other clinical decision rules were derived retrospectively. By analyzing the characteristics of patients who had an anaphylactic reaction, we were able to derive a rule to identify a low-risk group of biphasic reaction (any symptom of allergy) and clinically significant biphasic reaction (i.e. meeting the criteria for an anaphylactic reaction). These rules were created with the highest possible negative predictive sensitivities and values (VPNs).

The next step is to prospectively verify whether these rules maintain their sensitivity and negative predictive value with a different sample of patients from the same population pool. The first rule assesses the probability of clinically significant biphasic reactions (sensitivity of 90%, 7 variables; Table 3) and the second, all biphasic reactions (100%, 7 variable sensitivity; Table 4). Areas below the ROC curve were 0.896 and 0.874, respectively. Because the variables selected for each decision-making rule come from a regression model, the predicted probability of a biphasic reaction comes from the linear combination of selected variables. Depending on the coefficients calculated, each variable present in the patient will have a different weight in the decision.

TABLE 3: RETROSPECTIVELY DERIVED CLINICAL DECISION RULE FOR CLINICALLY SIGNIFICANT BIPHASIC REACTIONS

| | |
|----|--|
| 1. | ATCD allergy to a different agent than the one in question |
| 2. | Symptoms of diarrhea |
| 3. | ATCD allergy to the same agent as the one in question |
| 4. | Number of doses of O.R. in the emergency room |
| 5. | Food allergen (other than milk, egg, peanuts, seafood) |
| 6. | Number of doses of O.R. before emergency 1 |
| 7. | ENT symptoms |

TABLE 4: RETROSPECTIVELY DERIVED CLINICAL DECISION RULE FOR BIPHASIC REACTIONS (ALL SEVERITIES CONFUSED)

| | |
|----|---|
| 1. | Number of doses of O.R. in the emergency room |
| 2. | Epi doses data different from standard doses (ped: 0.01mg/kg, adult: 0.3-0.5mg) |
| 3. | Symptoms of diarrhea |
| 4. | ATCD allergy to a different agent than the one in question |
| 5. | Secondary anaphylactic reaction to iodine |
| 6. | Secondary anaphylactic reaction to a sting or bite |
| 7. | Secondary anaphylactic reaction to an unknown allergen |

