1. GOALS AND ASSUMPTIONS

The main objective of Phase 2 of our study is to validate prospectively and on a theoretical basis the rules of clinical decisions from previous phases of our research project. This will allow us to assess the internal validity of the different rules derived in the same three circles (Chicoutimi, Jonquière, Alma). In addition, the evaluation of the results will identify the most effective rule.

The hypothesis of this study is that one of the derived rules will, when applied to a cohort of patients prospectively, adequately identify (sensitivity maintained) patients at low risk of biphasic reaction following an anaphylactic reaction.

If the results of the Phase 2 study are successful, a phase 3 will be put forward. The objective of this third phase will be to apply the most effective rule in real time to patients who have undergone an anaphylactic reaction in different hospitals of the RIUSSS of the University of Sherbrooke, i.e. to complete the validation of the rule in a different population.

In the event of an inconclusive Phase 2 result for the three rules under study, the investigators propose to group the data from Phases 1 and 2 to attempt a final diversion of a new clinical decision rule. If this ultimate diversion is quite different from the previously tested rules and is clinically plausible, a new validation attempt will be made (details below).

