Based on the data, all three rules will be theoretically applied to all included patients. This will determine which patients would have been dismissed or observed and under what rule. Subsequently, the records of these same patients will be retrospectively analyzed to determine the occurrence of biphasic reaction after the initial visit. It will be particularly interesting to assess whether the biphasic reaction occurred during the emergency observation period.

As we seek to evaluate the effectiveness of diagnostic rules, statistical analyses will focus primarily on a study of sensitivity and specificity. In order to be able to properly characterize the different derived rules, it will also be relevant to obtain the predicted positive and negative values. Confidence intervals will be built around the proportions obtained. The choice of the best derived rule will be based on the sensitivity value obtained. Indeed, we seek to maximize this parameter in order to obtain the combination of variables that will allow us to use a rule to safely discharge patients with low risk of biphasic reaction. In the event that none of the rules maintain a fairly high sensitivity and/or negative predictive value, all Phase 1 and Phase 2 data will be jointly analyzed and a re-derivation test of a statistically stronger rule will be conducted, again using logistic regression models.

Considering that the sample size has been revised, the study schedule has also been revised. It is therefore more realistic for us to expect a period of at least 2 to 3 years to complete the data collection for this phase 2. However, we propose to do an interim analysis of the results at least once a year. Data collection is currently planned for 2020 and 2021 with an initial interim analysis in May 2020. The team is ready to extend the "recruitment" period as needed to reach the 553 patients needed. Data collection is currently well underway and the goal of recruiting 200 to 250 patients per year seems realistic.

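### The fallback re-derivation on pooled Phase 1 and 2 data names no optimism correction, so the new rule's reported performance is likely to look better than it is

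*Combined protocol and SAP*

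**What the plan says.** Under Methodological, Data analysis, the trigger is worded "In the event that none of the rules maintain a fairly high sensitivity and/or negative predictive value". In that case "all Phase 1 and Phase 2 data will be jointly analyzed". The method for the new rule is given only as follows: "a re-derivation test of a statistically stronger rule will be conducted, again using logistic regression models". Goals and Assumptions describes the same step for an inconclusive result on all three rules: "the investigators propose to group the data from Phases 1 and 2 to attempt a final diversion of a new clinical decision rule".

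The same paragraph of Goals and Assumptions adds a conditional safeguard. The new rule goes forward if it is "quite different from the previously tested rules and is clinically plausible, a new validation attempt will be made (details below". The details it points to are not in the document as supplied.

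Steps Taken gives the background. Of the two Phase 1 rules it says "These rules were created with the highest possible negative predictive sensitivities and values (VPNs". Their reported figures are "sensitivity of 90%, 7 variables; Table 3" for clinically significant reactions and "all biphasic reactions (100%, 7 variable sensitivity; Table 4" for all reactions, with AUCs of 0.896 and 0.874. No optimism correction is mentioned for these.

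No section names a bootstrap, cross-validation, hold-out sample, penalisation, variable-selection rule or cut-off rule for the re-derivation.

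**The concern.** When variables are selected, coefficients fitted and a cut-off chosen on the same patients, performance measured on those patients is optimistic. The optimism grows as events per candidate variable fall. The fallback is exposed on both counts: it uses every available patient, and biphasic reactions are rare.

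It is also reached only after the two regression-derived rules and the literature-based rule have all failed to perform well enough. It then returns to the same model family with no stated protection against the same kind of loss.

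At stake is how the new rule is judged. Its purpose is to identify patients who can safely leave early, so sensitivity is the figure that matters most. The plan expects at least 2 to 3 years to complete the present cohort. An uncorrected figure gives a poor basis for committing to another one. A re-derived rule that resembles the earlier rules has no stated validation at all.

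**Working it through.** **1. The plan's own figure.** Inputs from Sample size: sensitivity 0.98, precision 0.05, 95% confidence (z = 1.96), prevalence 0.06, 10% added for missing data.

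- Events: 1.96² × 0.98 × 0.02 / 0.05² = 30.1
- Patients: 30.1 / 0.06 = 501.95, rounded up to 502
- With 10% added: 502 × 1.10 = 552.2, rounded up to 553, as stated

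Phase 2 should therefore supply about 30 events (502 × 0.06) to 33 events (553 × 0.06).

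**2. Events per candidate.** The appendix questionnaire has 4 history, 4 allergen, 4 symptom and 6 treatment yes/no items, 18 in all. The plan gives no candidate list, so 18 is a working assumption. Phase 1 size is not stated, so a range is assumed. Pooled events = (553 + Phase 1 N) × 0.06.

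| Assumed Phase 1 N | Pooled events | Events per item (÷ 18) |
|---|---|---|
| 150 | 42 | 2.3 |
| 300 | 51 | 2.8 |
| 500 | 63 | 3.5 |
| 1,000 | 93 | 5.2 |

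Clinically significant reactions are a subset and would give fewer.

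**3. Simulated loss with selection to 7 variables.** Assumptions: 18 independent binary items, 6 of them real; 6% prevalence; logistic regression with backward selection to 7 (the size of each Phase 1 rule); cut-off set on the same data; 300 runs per setting; Phase 1 N of 150, 300 and 500. Entries are apparent value to value in new patients.

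| True AUC | Pooled N | AUC | Sensitivity, target 98% | Sensitivity, target 90% |
|---|---|---|---|---|
| 0.67 | 703 | 0.727 to 0.612 | 99.9% to 95.8% | 92.4% to 81.5% |
| 0.67 | 853 | 0.717 to 0.622 | 99.3% to 95.3% | 92.3% to 83.6% |
| 0.67 | 1,053 | 0.713 to 0.632 | 99.1% to 95.8% | 92.2% to 84.8% |
| 0.74 | 703 | 0.780 to 0.701 | 99.9% to 95.8% | 92.0% to 83.3% |
| 0.74 | 853 | 0.775 to 0.713 | 99.3% to 96.3% | 92.0% to 85.2% |
| 0.74 | 1,053 | 0.770 to 0.719 | 99.0% to 96.2% | 91.6% to 85.7% |

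The loss is about 3 to 4 points near 99% and about 6 to 11 points near 92%. With the cut-off set at 100% apparent sensitivity, the new-patient value is 96.0% to 98.4%, a loss of about 2 to 4 points. The AUC falls by 0.05 to 0.12.

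**4. Effect of selection.** Assumptions: 18 independent items, 5 real, true AUC 0.68, 6% prevalence, at least 97% apparent sensitivity required, 150 runs.

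| Pooled events | All 18 items kept | Backward selection to 7 |
|---|---|---|
| 42 | 98% to 88% | 98% to 92% |
| 51 | 98% to 90% | 99% to 94% |
| 62-63 | 98% to 93% | 99% to 95% |
| 92 | 98% to 94% | 99% to 97% |

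A separate repeat of the 18-item model, at 42, 49, 62 and 92 events, gave 89%, 91%, 93% and 95% in new patients from about 98% apparent.

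**5. Effect of a stronger true signal.** All 18 items, 5 real, about 98% apparent sensitivity, 200 runs. With 60 events the loss is about 5 points at true AUC 0.72 and 3.5 at 0.86. With 90 events it is about 3 and 2 points.

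Sensitivity fell in every setting. At about 98-99% apparent sensitivity the loss runs from roughly 2 points (92 events with selection, or 90 events at true AUC 0.86) to 10 points (42 events, all 18 items). For scale, the Sample size section plans for an accuracy of 5 points.

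**The case against.** The strongest reply is that the plan does not stop at the re-derived rule. It foresees a new validation, and data from new patients would expose any optimism. That stands where the validation is triggered, so a reader who infers that no validation is planned goes too far. But the promise covers only a rule that is different and plausible, and its details are absent. Potential Outcomes places live use in a Phase 3 with systematic follow-up, but speaks of a rule that proved effective in Phase 2, not of a re-derived one.

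Four other strong readings are tempting and should be resisted.

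- **That overfitting is certain, or that the regression is unpenalised.** The text says only that logistic regression will be used. It neither specifies nor excludes penalisation. The supportable wording is that optimism is likely unless corrected.
- **That the decision to validate rests on apparent performance.** The stated criteria are difference and plausibility. The fault is that no performance criterion is given.
- **That the loss can be sized on Phase 2 alone.** With 30 events and all 18 items, a simulation gives 99% apparent falling to 85%. The plan pools both phases, so that is not the proposed analysis.
- **That the main result is undermined.** The fallback is contingent and separate from the validation of the three existing rules.

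It is also fair that the size depends on chosen inputs. A strong true signal, more Phase 1 events or a very high cut-off each shrink the loss. The direction does not change.

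**Conclusion.** The point holds as a limited one. Followed as written, the fallback is likely to report optimistic sensitivity, NPV and AUC for the re-derived rule, because nothing corrects for selection, fitting and cut-off choice on the same patients. At about 98-99% apparent sensitivity the expected loss in new patients is roughly 2 to 10 points.

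That range rests on assumptions the documents do not settle: Phase 1 size (150 to 1,000 patients, giving 42 to 93 pooled events), the 18 questionnaire items as independent candidates, 5 or 6 real predictors, true AUC between 0.67 and 0.86, and the cut-off rule. NPV was not simulated; its optimism is inferred from the same mechanism.

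The gap in validation needs no assumption. It is conditional, has no performance threshold, lacks its promised details, and leaves out a re-derived rule that resembles the earlier ones. The point deserves correction before the data are analysed, but it concerns a contingent step.

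**What to change.** Add a paragraph to Data analysis stating that:

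- the candidate variables, selection rule and cut-off rule for any re-derivation are fixed in advance;
- the whole procedure (selection, model fit and cut-off choice) is repeated in each bootstrap resample;
- optimism-corrected AUC, sensitivity and NPV are reported beside the apparent values;
- the decision to launch a new validation uses the corrected figures as well as difference and plausibility;
- any re-derived rule, whether or not it resembles the earlier ones, is validated in new patients before use.

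Supply in Goals and Assumptions the validation details that it promises. Penalised regression is a reasonable option but not required: in a check, bootstrapping the whole procedure recovered most or nearly all of the gap.

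The cost is one paragraph, modest programming and a less favourable reported performance. The bootstrap itself needs no new patients. Validating a rule that resembles the earlier ones would need them, and the plan does not now provide for that.

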1. ETHICAL CONSIDERATIONS AND INSTITUTIONAL CONVENIENCE

No clinical decision rules will actually be applied to patients during this phase of the study. Doctors will therefore take care of patients according to their usual practice. In addition, the questionnaire will only be completed after the initial stabilization of the patient, and will not result in delay in its management. We therefore consider that the risk to patients associated with this study is negligible or non-existent.

To preserve the anonymity of patients, the questionnaires, once completed, will be placed in sealed envelopes. They will only be opened when the results are analysed by the doctors involved in the study. In addition, when counting the data, patients will be identified by a different random number, which will be associated with their file number. The "key file" of correlation between file numbers and identifier numbers will be securely retained by members of the search team.

The involvement of clinical staff will be minimal. The administrative officer will be responsible for putting the questionnaire sheet on the record of the user who presents himself with potential anaphylaxis when creating it. The officer will also be responsible, upon closing the emergency file, for removing the questionnaire sheet from the clinical file, ensuring that it is properly identified and keeping it in a secure stream for the study investigators..

The triage nurse, beyond her usual role of triage and identification of potential anaphylaxis cases, will also be responsible for attaching a questionnaire sheet to the file, weather permitting.

The attending physician, on the other hand, will only have to check, depending on the case, the appropriate boxes on the questionnaire sheet once his patient has stabilized.

1. SCHEDULE

Phase 2 will begin as soon as possible or in December 2019. Other steps will take place in the following months, such as:

| |
|---|
| 
October 2019:
 
 1. Writing the Phase 2 protocol 2. Asks the Ethics, Scientific and Institutional Convenience Committee of the Saguenay-Lac-Saint-Jean CIUSSS for approval. |
| 
November 2019:
 
 1. Introducing the study to emergency departments (department meetings) |
| 
December 2019
 
 1. Start of data collection |
| 
January and February 2020:
 
 2. Scholarship application 3. Review and Amendment of the Research Protocol (following the external evaluation requested by FRIPS) |
| 
February and March 2020:
 
 4. Submission of the amended protocol to the Ethics, Scientific and Institutional Convenience Committee of the CiUSSS of Saguenay-Lac-Saint-Jean for approval |
| 
April 2020:
 
 5. Statistical analysis of results (first interim analysis) |
| 
May 2020:
 
 6. Presentation of the study at the research day of the Department of MF/MU of the University of Sherbrooke |

| | |
|--------------------------|--|
| June 2020 to April 2021: | |
| 7. | Continued data collection |
| May 2021: | |
| 8. | Second interim analysis |
| 9. | Presentation of the progress of the study at the research day of the department of MF/MU of the University of Sherbrooke |
| End of 2021 | |
| 10. | Final Analysis or Request for Extension |
| 11. | Consideration of results and possible publication |
| 12. | Creating a poster and presenting it in various contexts (to be specified) |
| 13. | Planning for Phase 3 of the project |

1. POTENTIAL OUTCOMES

If one of the clinical decision rules is sufficiently effective during this phase of the study (phase 2), i.e. maintaining good sensitivity and negative predictive value, it can be applied in real time. If more than one rule is effective, the most easily applicable rule will be chosen. This will be done as part of a phase 3 study with systematic follow-up for each patient for whom the rule has been applied.

If Phase 3 proves it is conclusive, the rule demonstrates a strong negative predictive value during its actual clinical use and good external validity, and it will be disseminated on a larger scale. Thus, we hope to facilitate the management of anaphylaxis in the emergency room by allowing **the early and safe release** of many patients who have been treated for an anaphylactic reaction, ensuring that the risks of biphasic reactions are minimized.

The rule bearing the name of the geographic region from which it originates could help to spread the environment of the CIUSSS SLSJ. In addition, having received financial assistance and support from the MF/MU department of the University of Sherbrooke, the investigators will ensure that the name of the University and the Department they represent is clearly visible in their publication; also helping to spread the way of this institution.

13. Syed Mustansir Hussain Zaidi et Al., Sample size estimation of diagnostic test studies in health sciences, *Proc. 14th International Conference on Statistical Sciences*, Karachi, Pakistan, March 14-16, 2016, Vol. 29, pp. 239-246.

1. APPENDIX: QUESTIONNAIRE SHARED - Phase 2 study (validation)

To be filled for any patient with an anaphylactic reaction AFTER initial management but BEFORE discharge

Site of the visit: Chicoutimi Jonquière Alma

Date : _____

Time of arrival in the emergency room:

The time at which this questionnaire is completed:

| | |
|--|--|
| The patient meets the criteria for an anaphylactic reaction: yes no   | If answered no to the last question: the patient confirms exposure to an allergen and I believe that it will inevitably evolve towards an anaphylactic reaction. yes no   |
|--|--|

Time of onset of symptoms:

Exact time: - **ESTIMATED** time:

Hours of cob doses:

1^{is} _____, 2,^{and} _____, 3,^{and} _____, 4,^{and} _____, 5^{and} _____, 6,^{and} _____

History

ATCD allergy to an allergen other than the one involved. yes no

ATCD of allergy to the allergen involved. yes no

ANaphylaxis ATCD. yes no

Asthma ATCD. yes no

Allergen

Insect bite or bite. yes no

Iodine. yes no

Unknown allergen. yes no

Food allergen other than milk/peanuts/eggs/seafood. yes no

Symptoms

Severe symptoms (hypoTA, respiratory sx, vomiting, intubation, syncope, arrhythmias). yes no

ENT symptoms. yes no

Diarrhea. yes no

Time before symptom resolution - 40 minutes. yes no

Treatment

Time before the first dose of ear - 60 minutes. yes no

Number of doses of epi IM - 1. yes no

Number of ear doses before emergency room arrival. yes no

Number of ear doses in the emergency room. yes no

Epi doses data different from standard doses (ped: 0.01mg/kg, adult: 0.3-0.5mg). yes no

Administration of glucocorticoids. yes no

Section reserved for investigators

Rb. yes no

RBCS. oui non

[name]. yes no

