1. Sudden onset, with/without exposure to identified allergen, of skin and/or mucousness with at least 1 of 2:
 1. Respiratory disease (dyspnea, wheezing, stridor, hypoxemia, ...)
 2. HypoTA or Sx associated with a dysfunction of the target organs (hypotonia/collapse, syncope, incontinence, ...)
3. Probable allergen exposure and sudden onset (minutes to hours) of at least 2 of 4:
 1. Skin and/or mucousness (pruritus, rash, hives, etc.)
 2. Respiratory disease (dyspnea, wheezing, stridor, hypoxemia, ...)
 3. HypoTA or associated Sx (hypotonia/collapse, syncope, incontinence, ...)
 4. Persistent GI Sx (abdominal pain, vomiting, ...)
5. Sudden hypotension (minutes to hours) following known allergen exposure
 1. Children: 30% systolic decrease
 2. Adults: 30% decrease vs. basic personal systolic tension

There are no definitive predictors, but various factors of poor prognosis are recognized. These differ slightly between studies, but some seem to return quite systematically in the literature. First, the **severity of the reaction** appears to increase the risk of biphasic reaction. "Severe" means, reactions that initially required **1 dose of epinephrine**, those requiring a higher dose of epinephrine or an intravenous hydration bolus.⁸ Also, patients with **hypotension, pharyngeal edema or severe respiratory distress** upon arrival at the emergency department are among the reactions considered "severe"⁹. Patients with a total duration of **symptoms greater than 30 minutes** also appear to be at greater risk¹⁰. On the other hand, **delayed administration of epinephrine or a late presentation** to the emergency department would also increase the risk of adverse developments.¹¹ Finally, a **history of anaphylaxis** and exposure to an **unknown allergen** would be two additional risk factors for biphasic reaction¹².

It should be noted that most studies dealing with biphasic reactions exclude patients chronically taking corticosteroids, antihistamines, or beta-blockers, as well as patients on immunosuppressants⁶. It is therefore difficult to apply any conclusions to these populations.

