1. STEPS TAKEN

A review of the literature (phase 0; Rapid review) and phase 1 of the project (statistical derivation of two clinical decision rules) have already been completed. The initial "rapid review" literature review was to highlight the main elements that appeared to be predictors of a biphasic reaction. These elements led to the development of an initial clinical decision rule that included 7 variables (Table 1).

Table 1: CLINICAL DECISION RULE ORIGINALLY DEVELOPED FROM THE RAPID REVIEW OF THE LITERATURE

| |
|---|
| 
Promote an observation if one of the following is present:
 
1. Time before the first dose of 60min2. Severe symptoms (hypoTA, respiratory sx, vomiting, intubation, syncope, incontinence)3. Time before symptom resolution - 40 min4. Anaphylaxis ATCD5. Number of doses of EPI IM - 16. Asthma ATCD7. No administration of glucocorticoids |
|---|

Conflicting data in the literature review, a criterion included as exploratory in the "literature-based" rule

However, for the purpose of publishing our Phase 0 (literature review), the analysis of all articles included in the initial literature review (rapid review) was redone by another team member. As a result of this comprehensive review of each article, the literature review has moved from the "rapid review" to the "systematic review" type and minor changes have had to be made to the rule based on the literature review (below).

Table 2: CLINICAL DECISION RULE FROM SYSTEMATIC LITERATURE REVIEW

| |
|---|
| 
Promote an observation if one of the following is present:
 
1. Time before the first dose of 60min2. Severe symptoms (hypoTA, respiratory sx, vomiting, intubation, syncope, arrhythmias, diarrhea)3. Time before symptom resolution - 40 min4. Anaphylaxis ATCD5. Number of doses of EPI IM - 16. Unknown allergen7. No administration of glucocorticoids |
|---|

Conflicting data in the systematic literature review, a criterion included as exploratory in the "literature-based" rule

Thus, in terms of the criterion of severe symptoms of the initial anaphylactic reaction, we added arrhythmias, the presence of diarrhea and we removed incontinence. The asthma history criterion was removed from the rule and we added an unknown allergen.

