In the face of a case of anaphylaxis, the doctor will have to answer a short questionnaire developed with the variables present in each of the three rules (questionnaire available in appendix). The variables were randomly arranged on the questionnaire so that no rules could be recognized or inferred. If the doctor deems that a patient who does not yet present the anaphylaxis criteria, but in the absence of ahead, will eventually progress to real anaphylaxis, he or she will have to indicate it at the appropriate location on the questionnaire. Indeed, as mentioned above, these patients will be included in the study, but we will independently analyze the results of this sample to determine if they are different from the overall results in subgroup analyses.

The questionnaire will be available at several key locations, including in the paper-based resuscitation rooms in the three emergencies where data collection will take place. The questionnaire will also be systematically placed on the file of patients with suspected anaphylaxis at triage. The doctor will be required to complete the questionnaire anonymously, but will be required to provide the patient's file number. This will be done after the initial stabilization. After completing the questionnaire, the physician will simply be able to continue to care for the patient as he would have done in accord with his standard clinical practice. No decision rules will be applied to patients. The answers provided to

the questionnaire will therefore have no impact on the clinical decisions made by the treating physician. The research team will then review each of these files to assess whether or not there was a biphasic reaction and whether it was clinically significant (according to the NIAID/FAAN²criteria).

At the next emergency department meetings involved, doctors will be notified of the operation of the current study. Recalls will be made as required during the course of the study to ensure the involvement of the medical profession. Administrative officers and triage nurses will also be advised to add the questionnaire to all potential anaphylaxis files.

Data analysis

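### Three epinephrine items have no cut-off at biphasic onset and the form may be completed up to discharge, so treatment of an in-department recurrence can be scored as its predictor

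*Combined protocol and SAP*

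**What the plan says.** **When the form is completed.** The Appendix questionnaire gives a window: "To be filled for any patient with an anaphylactic reaction AFTER initial management but BEFORE discharge". The section on ethical considerations says "the questionnaire will only be completed after the initial stabilization of the patient". The data collection text under Methodological sets the same lower limit and continues: "After completing the questionnaire, the physician will simply be able to continue to care for the patient". Neither section sets an upper limit.

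**What counts as an outcome.** The file review looks for biphasic reactions, including those before the patient leaves: "It will be particularly interesting to assess whether the biphasic reaction occurred during the emergency observation period" (Methodological, data analysis).

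**What the items cover.** The background ties severity to the first episode in two places: "reactions that initially required" (Problem) and "in terms of the criterion of severe symptoms of the initial anaphylactic reaction" (Steps taken). The form repeats neither limit. Its items on ED doses (Tables 3 and 4), total intramuscular doses (Table 2) and non-standard dose (Table 4) do not say which doses count. The pre-arrival dose item (Table 3) ends at arrival and is not exposed.

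**What is recorded.** The form has fields for its completion time and for up to six dose times (the translation is unclear, but these appear to be epinephrine). It has no field for dose amounts or for biphasic onset time, and no analysis rule uses the recorded times.

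**How rules are judged.** "The choice of the best derived rule will be based on the sensitivity value obtained" (Methodological, data analysis). A rule goes forward if it succeeds in "maintaining good sensitivity and negative predictive value" (Potential outcomes).

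**The concern.** A predictor should be fixed before the outcome it predicts. Here the permitted completion window overlaps the outcome window. If a patient recurs in the ED, receives epinephrine for it, and the form is completed afterwards, the extra dose can enter the dose count. A patient whom the rule would have missed on the initial reaction alone may then be counted as detected.

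Only patients with a biphasic reaction can be affected in this way. Any upward shift therefore acts on sensitivity and, through fewer false negatives, on negative predictive value (NPV). For a rule meant to support early release, that is the unsafe direction of error.

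**Working it through.** **1. Whether the windows overlap.**
- Earliest completion: after initial stabilization (Methodological; Ethical considerations).
- Latest completion: discharge (Appendix). The sheet stays in the file until the emergency file is closed (Ethical considerations).
- Usual observation: four to six hours (Problem).
- A biphasic reaction follows resolution of the first reaction (Problem). One item asks about time to symptom resolution against 40 minutes, so it can be answered only after resolution or once 40 minutes have passed.

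A form completed late in the stay is within the plan and can follow a recurrence.

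**2. Direction, rule by rule.**
- *Table 4 rule.* The note after Table 4 says that not repeating doses, and giving standard doses, each lowered the likelihood. Extra doses therefore push towards positive. The weights and cut-off are not given, so whether one item flips the rule cannot be known. The non-standard-dose item changes only if the recurrence dose was itself non-standard and the earlier doses were standard.
- *Literature rule (Table 2).* Any one item makes it positive. The comparison sign in the total-dose item is unreadable. A flip needs that item to mean more than one dose and no other item to be positive. The item on absence of glucocorticoid treatment works the opposite way: steroids given for the recurrence and scored late would turn it negative.
- *Table 3 rule.* The direction for ED doses is not stated.

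**3. The plan's own figure.** Inputs from the sample size text: sensitivity 0.98, precision 0.05, prevalence 0.06, 95% confidence, 10% added.
- Buderer: n = z² × Se × (1 − Se) / (d² × prevalence) = 1.96² × 0.98 × 0.02 / (0.05² × 0.06) ≈ 502.
- 502 × 1.10 = 552.2, rounded up to 553. This matches the plan.
- Expected biphasic reactions: 553 × 0.06 = 33.2; without the allowance, 502 × 0.06 = 30.1.

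**4. Limit on sensitivity.** Let s be true sensitivity and f the share of missed cases reclassified. Apparent sensitivity = s + (1 − s) × f, so the expected rise cannot exceed 1 − s. At s = 0.98 the cap is 2 points. The documents do not give f. For assumed values of 10%, 25% and 50%, 98% would read 98.2%, 98.5% and 99.0%.

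**5. One case.** 1/33 = 3.0 points (1/30 = 3.3). With exact (Clopper-Pearson) 95% intervals, 32/33 = 97.0% (84.2 to 99.9) would read 33/33 = 100% (89.4 to 100). This step is larger than the 2-point cap because the cap is an expectation: at 98%, the expected number of missed cases is only 33 × 0.02 = 0.66.

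**6. Limit on NPV.** NPV = sp × 0.94 / (sp × 0.94 + (1 − s) × 0.06). Specificity (sp) is not given; 0.3, 0.5 and 0.7 are assumed. At s = 0.98, NPV = 99.58%, 99.75% and 99.82%, so the largest possible rise is 0.42, 0.25 and 0.18 points.

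**The case against.** **The planned order already avoids it.** The text describes stabilizing the patient, completing the form, then continuing care. Discharge reads as a backstop. This stands as a description of intent and means the planned order does not itself produce the bias. It does not close the window, because a late form still complies with the plan and no rule says how to treat it.

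**The times are on the form.** Affected doses could be identified at file review. True, but only if onset time is abstracted and a rule says to use it. Neither is written.

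**The exposed group is small.** A case must recur before discharge, receive epinephrine for it, have the form completed afterwards and cross the cut-off. The Problem section says that recurrences can come up to 72 hours later and are usually milder. This stands, and it is why no frequency can be claimed.

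**Stronger readings that the documents do not support.**
- A reader might infer that all three rules are inflated. Direction is supported only for Table 4, and the glucocorticoid item can pull the literature rule the other way.
- A reader might take the Phase 1 sensitivity of 90% and infer room for a 10-point rise. That figure belongs to the Table 3 rule, whose direction is not stated. The Table 4 rule had 100% in Phase 1; at that value no missed cases exist to reclassify.
- A reader might infer that the bias would decide which rule is adopted. Potential outcomes says that among effective rules the simplest to apply is chosen, and a Phase 3 with systematic follow-up comes before wider use.

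**Conclusion.** The point holds as a possible bias that the written plan leaves open, not as an expected one. The completion window and the three unbounded dose items together let treatment of an in-ED recurrence be scored as a predictor of it.

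An upward shift is supported for the Table 4 rule, subject to its unstated weights, and possible for the literature rule under the conditions above. For the Table 3 rule nothing can be said. At the planning sensitivity of 98%, the expected rise is at most 2 points, and the rise in NPV at most 0.2 to 0.4 points (specificity assumed at 30 to 70%). With about 33 events, a single reclassified case can still turn 97.0% into 100%. These figures rest on the planned 6% prevalence for biphasic reactions of any severity.

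This calls for a minor, low-cost improvement, best settled before the final analysis.

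**What to change.** 1. Abstract the time of biphasic onset in the file review already planned.
2. In the primary analysis, count only epinephrine doses timed before onset, for every form. Use the recorded dose times, and the chart where a time is missing. Use the chart for dose amounts, which the form does not record.
3. Keep forms completed after onset and report how many there are.
4. State on the form that dose, symptom (including ENT and diarrhea) and treatment items refer to the initial reaction only. For forms completed after onset, apply the same definition to the symptom and glucocorticoid items from the chart, by a written rule and by someone who does not know the rule result. Old and new forms then share one definition in the primary analysis.

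**Cost.** A few words on the form, one abstracted field, a short addition to the analysis text and a small re-scoring task (about 33 events expected, fewer of them with late forms). Collection began in December 2019, so the new wording reaches later forms only; the analysis rule and re-scoring cover the earlier ones. The sample size of 553 is unchanged. Estimated sensitivity may come out slightly lower.
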